8.3 ADVERSE EVENTS AND SERIOUS ADVERSE EVENTS

8.3.1 DEFINITION OF ADVERSE EVENTS (AE)

Potential risks to research subjects are: 1. Intracranial hemorrhage secondary to re-perfusion injury; 2. Stroke; 3. Seizures; 4. Extravasation of contrast secondary to injury to cervical ICA during the procedure; and 5. Contrast allergy. Strategies to mitigate risks to subjects in the trial include 1) exclusion of subjects with COICA type D, 2) performing the procedure only by the PI, 3) strict perioperative blood pressure management to minimize hypoperfusion pre-procedure (maintain MAP \geq 80mmHg and \leq 120mmHg) and hyper-perfusion post procedure maintain MAP \leq 80mmHg and \geq 60mmHg, 4) admission to neuro-intensive critical for management post procedure, and 5) use of IV maintenance dose Tirofiban immediately post procedure as a monotherapy for the first 24 hours (no aspirin or clopidogrel) to reverse the effect of anti-platelet effect within 90 minutes in case of dreaded intracranial hemorrhage secondary hyper-perfusion (from our series, no subjects suffered intracranial hemorrhage). If the subject is with no signs or symptoms of intracranial hemorrhage, then at the end of 24 hours, the subject will be given a loading dose of clopidogrel (600 mg) and aspirin (325mg) and Tirofiban continued for another 2 hours in order for the loading dose of aspirin and clopidogrel to reach therapeutic effect

8.3.2 DEFINITION OF SERIOUS ADVERSE EVENTS (SAE)

Adverse Event (AE) Reporting:

Any potential adverse event or a serious adverse event mentioned above will be reported during the trial. An AE will be defined as any unfavorable and/or unintended sign, symptom, or injury temporally associated with the procedure or other study medication. A serious adverse event (SAE) is defined as any untoward/undesirable adverse experience related to a study intervention/medication that results in any of the following outcomes: 1) death; 2) a life-threatening adverse experience; 3) need for additional surgery; 4) a permanent or significant disability/incapacity; 5) important medical events that may not result in death, be life-threatening, or require additional surgery.

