4 STUDY DESIGN

4.1 OVERALL DESIGN

Primary Hypothesis:

Revascularizing symptomatic chronically occluded cervical ICA (COICA) using endovascular techniques will significantly improve cognitive outcome.

Primary Objective:

To test the hypothesis that endovascular revascularization of COICA (via endovascular techniques) improves significantly cognitive function assessed by a specifically designed battery of 14 cognitive tests including the MoCA.

Secondary Objectivs:

To test the safety of endovascular revascularization of chronically occluded ICA.

Tertiary/Exploratory Objectives:

To test the hypothesis that subjects with symptomatic COICAs and mild/moderate cognitive dysfunction have the following biomarkers:

- A) increased MTT or TTP on CTP in the ipsilateral side of the occluded ICA specifically in the MCA territory when compared to the opposite unaffected hemisphere
- B) Presence of lactate and decreased Naa/Cr in the watershed area (specifically centrum semiovale) on 1H-MRI-spectroscopy, and
- C) Decreased size of the hippocampus and amygdala on MRI.

Primary endpoints:

Cognitive outcome at 12-month follow-up assessed mainly by a specifically designed battery of 14 cognitive tests including MoCA.

Secondary endpoints:

1. Safety: Occurrence of Stroke, Cerebral Hemorrhage, or Death

Exploratory endpoints:

Biomarkers:

- A) The presence/absence of lactate on 1H-MRI spectroscopy in centrum semiovale in the ipsilateral side of COICA;
- B) The change in size of amygdala and hippocampus in the ipsilateral side of COICA.
- C) Improvement/ normalization of MTT and/or PTT on CTP specifically in the ipsilateral MCA territory.
- D) subgroup difference (Gender)

Study Design:

This is a phase 2 randomized single-center open label clinical trial with randomization of 1:1 to either best medical management vs. best medical management and endovascular revascularization of COICA. Subjects who meet all inclusion criteria but have a normal CTP may be included in the unrandomized prospective observational 3rd arm.

Intervention: Surgical intervention - endovascular balloon angioplasty and stenting

Protocol:**Screening, Enrolling, & Randomization:**

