8.3.3 CLASSIFICATION OF AN ADVERSE EVENT

8.3.3.1 SEVERITY OF EVENT

All adverse events (AEs) will be collected, recorded, and analyzed. Safety oversight for this study will be provided by both the DSMB and an independent Medical Safety Monitor ([name]). All AEs will be classified as related to the intervention based on severity, relatedness and outcome.

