8.3.5 ADVERSE EVENT REPORTING

Safety oversight for this study will be provided by both the DSMB and an independent Medical Safety Monitor ([name]). Reports will be done of comparison of the intervention groups every 10 patients to the DSMB.

Data and Safety Monitoring Board [DSMB]:

The DSMB will be appointed by the NIA to monitor the performance of the study. The Steering Committee will prepare regular reports summarizing patient accrual and the morbidity and mortality experienced in the study. The DSMB will also review the cumulative outcome data at regular intervals (every 6 months).

Stopping rules or safety triggers for the study:

The occurrence of the following potential side effects and risks associated with procedure will trigger prompt reporting and review by the DSMB to discuss the events and decide on the continuation of the trial.

The following adverse events will be reported to the DSMB: 1) Any intracranial hemorrhage within 72 hours post procedure, 2) Any stroke within 30 days post procedure; 3) Any seizure within 72 hours post procedure; and 4) Any injury to the cervical ICA during the procedure.

Based on complication rates in the trial to date (June 2021), the occurrence of one additional event in these categories will trigger a suspension of enrollment in the trial and meeting of the DSMB to discuss the events and decide on the continuation of the trial.

Safety oversight for this study will be provided by both the DSMB and the Independent Medical Safety Monitors.

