8.3.6 SERIOUS ADVERSE EVENT REPORTING

AEs will be reported as they occur to the medical monitor. Safety oversight for this study will be provided by both the DSMB and an independent Medical Safety Monitor ([name]). Serious AEs will be reported to the DSMB and IRB as required.

Any potential adverse event or a serious adverse event mentioned above will be reported during the trial. An AE will be defined as any unfavorable and/or unintended sign, symptom, or injury temporally associated with the procedure or other study medication. A serious adverse event (SAE) is defined as any untoward/undesirable adverse experience related to a study intervention/medication that results in any of the following outcomes: 1) death; 2) a life-threatening adverse experience; 3) need for additional surgery; 4) a permanent or significant disability/incapacity; 5) important medical events that may not result in death, be life-threatening, or require additional surgery.

Study Monitoring

Local IRB monitors will conduct yearly monitoring visit. Review of the protocol and all data collection forms will be conducted, confirming the investigators' compliance and thereby ensuring appropriate and accurate data collection, regulatory committee approval, and informed consent procedures. Any minor concerns in data collection issues will be dealt with by the IRB. All significant concerns regarding either data collection or the nature of an investigator's participation which are not immediately solved will be reported by the IRB designated monitor and further evaluated by the IRB. Should an investigators deviate from the study protocol, the IRB will raise the issue with the Steering Committee, which will determine an appropriate course of action.

Participant Confidentiality

All imaging studies (MRA, CTA, and/or DSA), case report/evaluation forms, laboratory specimens, and other records will be de-identified and assigned Study Identification Number (SID) to maintain subject confidentiality. All records will be kept in a secure and locked file cabinet with keys to this cabinet only kept by the PI and/or nurse research coordinator. No clinical information will be shared or released without the written permission/consent of the patient, except as necessary for minoring by the IRB.

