9.4.3 ANALYSIS OF THE SECONDARY ENDPOINT(S)

The safety measures of occurrence of Stroke/TIA, cerebral hemorrhage, or death will be analyzed as frequency within the 30-day post-procedure period. Analysis will be done in aggregate of the events combined and individually using a Kaplan-Meier survival estimation with a Logrank test. Adjustment for age, etiology of ischemia, and side of occlusion will be done using a Cox Model Regression. A two-sided type I error rate of 0.05 will be used.

Analysis of the Tertiary/exploratory Endpoint

Tertiary/exploratory endpoints will be analyzed individually. The presence/absence of lactate will be estimated by a proportion and evaluated using a Fisher's Exact Test. The change in sizes of amygdala and hippocampus in the ipsilateral side of COICA will be using a T-Test of the difference. Improved and/or normalization of MTT and/or PTT on CTP specifically in the ipsilateral MCA territory will be analyzed using a T-Test.

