9.4.4 SAFETY ANALYSES

Event rates by treatment group will be reported with 95% confidence intervals. The distribution by severity will be compared. Kaplan-Meier time to event curves will be done for AEs and deaths. Logrank tests will be performed.

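### The SAE definition requires relatedness to a study intervention or medication, so serious disease-related events can escape SAE reporting to the DSMB and IRB and may be captured unevenly between arms

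*Combined protocol and SAP*

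**What the plan says.** The SAE definition in 8.3.2 reads: "A serious adverse event (SAE) is defined as any untoward/undesirable adverse experience related to a study intervention/medication". A list of serious outcomes follows. An event must meet both parts, relatedness and a listed outcome. Sections 2.3.3, 8.3.6 and 8.3.7 repeat the definition.

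The AE definition in 8.3.2 is wider but still anchored: "An AE will be defined as any unfavorable and/or unintended sign, symptom, or injury temporally associated with the procedure or other study medication". Section 8.3.3.1 adds "All adverse events (AEs) will be collected, recorded, and analyzed" and lists relatedness among the items used to classify an AE.

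On reporting, 8.3.6 says "Serious AEs will be reported to the DSMB and IRB as required", and that AEs go to the medical monitor as they occur. Section 8.3.5 says "Reports will be done of comparison of the intervention groups every 10 patients to the DSMB".

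On analysis, the secondary endpoint in 4.1 is "Safety: Occurrence of Stroke, Cerebral Hemorrhage, or Death". Section 9.4.3 adds TIA and a window: "The safety measures of occurrence of Stroke/TIA, cerebral hemorrhage, or death will be analyzed as frequency within the 30-day post-procedure period". Section 9.4.4 says "Event rates by treatment group will be reported with 95% confidence intervals", and plans Kaplan-Meier curves and logrank tests for AEs and deaths. It does not name SAEs as an analysis set.

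**The concern.** An SAE is usually identified by its outcome, and cause is then recorded as a separate judgement. Here the causal judgement decides whether the event is an SAE at all. That matters in this trial because the control arm's main expected serious event, an ischemic stroke from the occlusion itself, has no obvious link to the study drugs. A stroke soon after stenting is readily called related.

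Two things are at stake. The first is oversight: serious events judged unrelated need not reach the DSMB and IRB as SAEs. The second is evenness of capture. The relatedness judgement is made in an open-label trial, and 6.2 limits blinded assessment to cognition, MRI and the exploratory endpoints. Recurrent stroke is also an outcome that 2.3.2 says revascularization may prevent, so the oversight bodies need to see it in both arms.

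**Working it through.** **1. Follow one event through the text.** Take a medical-arm subject with a disabling ischemic stroke at month 5, judged unrelated to aspirin, clopidogrel or statin.

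- SAE (8.3.2): the outcome criterion is met and relatedness is not. It is not an SAE, so the SAE route in 8.3.6 does not apply.
- DSMB triggers (2.3.3, 8.2, 8.3.5): the four triggers are intracranial hemorrhage or seizure within 72 hours of the procedure, stroke within 30 days of it, and cervical ICA injury during it. None can fire for a subject who had no procedure. The 20% rate rule in 2.3.3 counts the same events.
- Rapid reporting (2.3.3): the 3-hour and 24-hour steps are written for events during surgery.
- Unanticipated problems (8.4.1): the definition is tied to a device, so it does not cover this stroke.
- AE (8.3.2): this turns on whether a stroke while taking daily study medication counts as temporally associated with it. A broad reading includes it, but the text does not say so. If included, it goes to the medical monitor.

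Every expedited route to the DSMB written for a named or serious event is therefore closed or procedural.

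**2. See which analyses depend on the definition.**

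| Use | Set of events | Filtered by relatedness? |
|---|---|---|
| SAE reporting (8.3.6) | SAEs | Yes |
| AE rates and curves (9.4.4) | AEs | No, but tied in time to procedure or medication |
| Deaths (9.4.4) | Deaths | No |
| Secondary endpoint (4.1, 9.4.3) | Stroke (with TIA in 9.4.3), hemorrhage, death | No |
| DSMB group comparison (8.3.5) | Not stated | Not stated |

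Uneven capture can enter SAE listings directly. It can enter the 9.4.4 AE analysis through the AE wording. Section 2.3.3 adds to this: intervention subjects are checked daily in hospital for adverse events, while medical-arm visits are described as checks of medication, compliance and side effects.

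**3. Size the exposure.** Inputs:

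- Arm size: 9.2 gives 34 before dropout and 38 after. The 34 reproduces with a two-sample t-test (difference 2, SD 2, two-sided 0.05, power 80%): 16.7, so 17 per arm. With 10% dropout, 34 / 0.90 = 37.8, so 38, or 19 per arm.
- Any-stroke risk on medical therapy: 7-10% per year (2.1).

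Expected control-arm strokes in 12 months, with 19 subjects fully followed:

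- 19 × 0.07 = 1.33
- 19 × 0.10 = 1.90

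Chance of at least one:

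- 1 − 0.93^19 = 0.75
- 1 − 0.90^19 = 0.86

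Expected in 30 days, assuming constant hazard, with p30 = 1 − (1 − r)^(30/365.25):

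- r = 0.07: 19 × p30 = 0.11
- r = 0.10: 19 × p30 = 0.16

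At least one control-arm stroke in the year is therefore likely. Most expected strokes fall after day 30: 1 − 0.11/1.33 and 1 − 0.16/1.90 are both about 92%. That second fact comes from the window in 9.4.3, not from the SAE definition. It matters here only because later non-fatal strokes have AE and SAE capture as their main written route.

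**The case against.** The strongest reply is that no planned between-arm analysis uses SAEs, and this stands. The secondary endpoint counts named events whatever their cause, and 9.4.4 analyzes AEs and deaths. The AE definition asks for association in time, not causality. Medical-arm subjects take study medication daily (6.1.1), so their strokes can qualify as AEs. Section 8.3.3.1 already classifies AEs by relatedness. The DSMB also receives regular morbidity and mortality summaries and reviews cumulative outcome data every 6 months, so it is not dependent on SAE reports alone.

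A reader might infer that the between-arm safety comparison is biased, and biased against the procedure. The documents do not support that. The relatedness condition applies to both arms: a late disease-related stroke in the surgical arm is equally outside the definition, and a control-arm hemorrhage on dual antiplatelet therapy could be judged related and counted. Nor does any section say that the comparison made every 10 patients uses SAEs. A reader might also take the 1.3-1.9 strokes as the number missing from a comparison. They are not. A stroke inside the 9.4.3 window counts in the secondary endpoint whatever its SAE status, and one outside it is excluded by the window.

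What the reply does not answer is reporting. A serious event judged unrelated is not an SAE under a definition stated four times, and periodic summaries do not replace event-level reporting. It also leaves open whether the AE wording will be applied alike in an arm with a procedure and an arm without one.

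**Conclusion.** The point holds for safety reporting and, less certainly, for evenness of capture. As written, a serious disease-related event judged unrelated is not an SAE in either arm and can escape SAE reporting to the DSMB and IRB. The specific DSMB triggers do not fill the gap for subjects without a procedure. SAE listings may be uneven between arms, and the 9.4.4 AE rates and curves may be too if the AE wording is read narrowly. The direction and size of any imbalance cannot be derived from the documents.

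The secondary endpoint and the analysis of deaths are not biased by this definition, and the sample size is unaffected.

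About 1.3-1.9 control-arm strokes in 12 months is the scale of what SAE reporting could miss, if every one were judged unrelated. It assumes 19 controls followed for the full year at the protocol's own 7-10% risk. With arms this small, one or two events can change how an SAE listing reads.

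**What to change.** Change the wording in 2.3.3, 8.3.2, 8.3.6 and 8.3.7:

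- Define an AE as any untoward occurrence from randomization to the end of follow-up in any arm, with enrollment as the starting point for the non-randomized third arm.
- Define an SAE by the listed outcomes, regardless of relationship to the intervention or medication.
- Record relatedness as a separate attribute for both AEs and SAEs.

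State in 9.4.4 and 8.3.5 that the event rates, time-to-event curves and DSMB group comparisons use all-cause events. Related events can be tabulated in addition.

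The cost is an edit in these sections, a matching case report form field and a few more SAE forms. Events already screened out under the present wording would need to be reviewed and reclassified, so that the listings use one definition throughout.

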8.3.3 CLASSIFICATION OF AN ADVERSE EVENT

8.3.3.1 SEVERITY OF EVENT

All adverse events (AEs) will be collected, recorded, and analyzed. Safety oversight for this study will be provided by both the DSMB and an independent Medical Safety Monitor ([name]). All AEs will be classified as related to the intervention based on severity, relatedness and outcome.

8.3.3.2 EXPECTEDNESS

Potential risks to research subjects are: 1. Intracranial hemorrhage secondary to re-perfusion injury; 2. Stroke; 3. Seizures; 4. Extravasation of contrast secondary to injury to cervical ICA during the procedure; and 5. Contrast allergy, 6. carotid fistula, 7. Radiation exposure

8.3.4 TIME PERIOD AND FREQUENCY FOR EVENT ASSESSMENT AND FOLLOW-UP

Strategies to mitigate risks to subjects in the trial include 1) exclusion of subjects with COICA type D, 2) performing the procedure only by the PI, 3) strict perioperative blood pressure management to minimize hypoperfusion pre-procedure (maintain MAP \geq 80mmHg and \leq 120mmHg) and hyper-perfusion post procedure (maintain MAP \leq 80mmHg and \geq 60mmHg), 4) admission to neuro-intensive critical for management post procedure, and 5) use of IV maintenance dose Tirofiban immediately post procedure as a monotherapy for the first 24 hours (no aspirin or clopidogrel) to reverse the effect of anti-platelet effect within 90 minutes in case of dreaded intracranial hemorrhage secondary hyper-perfusion (from our series, no subjects suffered intracranial hemorrhage). If the subject is with no signs or symptoms of intracranial hemorrhage, then at the end of 24 hours, the subject will be given a loading dose of clopidogrel (600 mg) and aspirin (325mg) and Tirofiban continued for another 2 hours in order for the loading dose of aspirin and clopidogrel to reach therapeutic effect.

All AEs will be followed until resolution with treatment by best medical or surgical management.

8.3.5 ADVERSE EVENT REPORTING

Safety oversight for this study will be provided by both the DSMB and an independent Medical Safety Monitor ([name]). Reports will be done of comparison of the intervention groups every 10 patients to the DSMB.

Data and Safety Monitoring Board [DSMB]:

The DSMB will be appointed by the NIA to monitor the performance of the study. The Steering Committee will prepare regular reports summarizing patient accrual and the morbidity and mortality experienced in the study. The DSMB will also review the cumulative outcome data at regular intervals (every 6 months).

Stopping rules or safety triggers for the study:

The occurrence of the following potential side effects and risks associated with procedure will trigger prompt reporting and review by the DSMB to discuss the events and decide on the continuation of the trial.

The following adverse events will be reported to the DSMB: 1) Any intracranial hemorrhage within 72 hours post procedure, 2) Any stroke within 30 days post procedure; 3) Any seizure within 72 hours post procedure; and 4) Any injury to the cervical ICA during the procedure.

Based on complication rates in the trial to date (June 2021), the occurrence of one additional event in these categories will trigger a suspension of enrollment in the trial and meeting of the DSMB to discuss the events and decide on the continuation of the trial.

Safety oversight for this study will be provided by both the DSMB and the Independent Medical Safety Monitors.

8.3.6 SERIOUS ADVERSE EVENT REPORTING

AEs will be reported as they occur to the medical monitor. Safety oversight for this study will be provided by both the DSMB and an independent Medical Safety Monitor ([name]). Serious AEs will be reported to the DSMB and IRB as required.

Any potential adverse event or a serious adverse event mentioned above will be reported during the trial. An AE will be defined as any unfavorable and/or unintended sign, symptom, or injury temporally associated with the procedure or other study medication. A serious adverse event (SAE) is defined as any untoward/undesirable adverse experience related to a study intervention/medication that results in any of the following outcomes: 1) death; 2) a life-threatening adverse experience; 3) need for additional surgery; 4) a permanent or significant disability/incapacity; 5) important medical events that may not result in death, be life-threatening, or require additional surgery.

Study Monitoring

Local IRB monitors will conduct yearly monitoring visit. Review of the protocol and all data collection forms will be conducted, confirming the investigators' compliance and thereby ensuring appropriate and accurate data collection, regulatory committee approval, and informed consent procedures. Any minor concerns in data collection issues will be dealt with by the IRB. All significant concerns regarding either data collection or the nature of an investigator's participation which are not immediately solved will be reported by the IRB designated monitor and further evaluated by the IRB. Should an investigators deviate from the study protocol, the IRB will raise the issue with the Steering Committee, which will determine an appropriate course of action.

Participant Confidentiality

All imaging studies (MRA, CTA, and/or DSA), case report/evaluation forms, laboratory specimens, and other records will be de-identified and assigned Study Identification Number (SID) to maintain subject confidentiality. All records will be kept in a secure and locked file cabinet with keys to this cabinet only kept by the PI and/or nurse research coordinator. No clinical information will be shared or released without the written permission/consent of the patient, except as necessary for minoring by the IRB.

